
Importantly, the benefits of intracranial pressure (ICP) monitoring must be weighed against the associated risks and complications. The risks of ICP monitoring are related to the degree of invasiveness, the location of the device, the presence of systemic infections, the need to restrict patient movement, and monitoring drift or artificially low readings. Complications include infection, hematomas, epilepsy, cerebral puncture, cranial nerve palsies, and CSF leaks. In general, the incidence of complication has been quoted as from 1.1% to 7.7%.²⁸⁻³²

A major motivating factor in our routine use of postoperative ICP monitoring is that clinical parameters (for example, blood pressure, neurological status, pulse, and respiration) are not always reliable markers of increased ICP or impending neurological deterioration secondary to complications.^{10,33} Moreover, some authors have showed the safety of ICP monitoring in the posterior fossa.^{1,21,23-26}

AIMS OF THE STUDY

The goal of this study is to test whether direct infratentorial monitoring is a more efficacious method for detecting dynamic changes in the operative compartment and whether it is safe, in view of the critical structures within the region.

The motivation behind this study is to determine the value of ICP and brain tissue oxygenation monitoring (LICOX) in the infratentorial compared to the supratentorial space in patients with posterior fossa lesions. Our aim is also the immediate detection of any pertinent complications that are related to mass effect or swelling within the posterior fossa, leading to subsequent prompt intervention in these patients. With this in mind, postoperative multimodal neuromonitoring is a standard procedure at our intensive care unit. The additional intracranial infratentorial monitoring most likely is the most sensitive way to detect any relevant complications or lesions that may result in irreversible sequelae.

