- 4) facilitate the neurointensive care of these patients including ventilatory support, the use of positive end-expiratory pressures, continued osmotherapy, and patient positioning; ultimately
- 5) better understand of pathophysiological processes with
- 6) immediately identify of complications with subsequent prompt intervention if needed.

QUESTIONS

- * Is infratentorial multimodal neuromonitoring safe and feasible, and necessary?
- * Do data assessed by multimodal monitoring in the posterior fossa correlate with data from the supratentorial compartment?
- * Is infratentorial multimodal neuromonitoring able to timely predict complications such as local swelling, mass effect, vasospasm, ischemia, or infarction?
- * Is infratentorial multimodal neuromonitoring of value in daily clinical practice?

HYPOTHESES

- The intracranial multimodal monitoring in the posterior fossa is safe and feasible, without any increased risk due to additional probes.
- Data generated by infratentorial multimodal neuromonitoring do not completely correlate with data from standardized supratentorial multimodal neuromonitoring. There are significant differences in ICP- or brain tissue oxygenation values between the supratentorial and infratentorial compartments.
- The infratentorial multimodal monitoring immediately detects all relevant complications related to posterior fossa lesions including mass effect, local swelling, postoperative hematoma, ischemic events, decrease in the blood flow, vasospasm and inadvertent or prolonged vessel occlusion, or infarction, resulting in prompt therapeutic intervention if necessary.
- Additional information from infratentorial probes facilitate to maintain the critical patients including ventilatory support, the use of positive end-expiratory pressures, continued osmotherapy, and patient positioning.

CLINICAL RELEVANCE

Our prospective study can provide better guidance and optimization of clinical therapy through a comprehensive assessment of patients harboring posterior fossa lesions.

This study has very high potential to generate a new intellectual property, to yield discoveries improving the prediction of complications and monitoring the effects of treatments. The data will offer better understanding of pathophysiological mechanisms in posterior fossa lesions.

STUDY DESIGN

METHODS

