In phase I of the study 15 patients with posterior fossa lesions who require prolonged neurointensive care and in which any intracranial invasive intervention is indicated regardless of used technique or treatment modality will be enrolled in the study. The indication for posterior fossa lesion treatment will be decided on a case-by-case basis by our neurosurgical team irrespective of the study.

The study will start as a monocentric clinical trial (pilot study), and subsequently in phase II the study is planned to be continued as a multicentric trial.

In the majority of patients, ICP- and LICOX sensors are usually placed in the right frontal lobe and/or at the site of the lesion. In case of posterior fossa surgery, additional probes (ICP / LICOX) will be placed into the surgical field.

The neuromonitoring data will be recorded and analyzed. Additionally, demographic data, all treatment-related complications, and management of intracranial hypertension will be recorded.

All adverse effects will be noted and reported, even if no clinical consequence will ensue. Non-neurological complications such as cardiopulmonary complications will be documented separately.

After the invasive treatment of the posterior fossa lesion, all patients will undergo CT and/or MRI as standard of care within 72 hours after the intervention (the acute phase) as a protocol for detection of procedure-related complications. As standard of care, an additional follow-up MRI will be performed if needed. In stable patients a preoperative MRI will also be performed before invasive treatment

The following outcomes will be evaluated and analyzed: mean ICP, ICP pulse amplitude, respiratory waves, slow waves and the RAP (compensatory reserve) index of supra- and infratentorial ICP signals, transtentorial difference, brain tissue oxygenation, blood saturation, ASTRUP, and further vital parameters, peri- and postoperative morbidity and mortality, procedure-related morbidity including infection, hematomas, epilepsy, cerebral puncture, cranial nerve palsies, and CSF leaks, perioperative cerebral ischemia, long-term neurological morbidity and mortality, and overall neurological outcome.

Institutional review board will be obtained by the Ethics Committee of the Medical University Innsbruck, Austria. Informed consent will be acquired from all patients for participation in the study during the study period according to local requirements.

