All patients suffering from symptomatic posterior fossa lesions are first treated and stabilized in the emergency room and/or at the ICU. After the initial imaging (in most cases CT/CTA), if necessary, patients are transported to the OR and/or the angiosuite. After treatment, regardless of the used treatment modality and possibly after implementation of invasive multimodal neuromonitoring according to contemporary guidelines by patient impaired consciousness (e. g., with GCS≤8), implantation of multimodal neuromonitoring is performed – please find the details in the study protocol TIBI-study (AN2014-0201 339/4.6 – microdialysis, tissue perfusion measurement, ICP-measurement, LICOX) the patients are transported to the neurosurgical or neurological ICU. In each patient, MRI including ³¹P-MRS will be performed at different stages of treatment (the indication for neuroimaging will be decided on a case-by-case basis). As mentioned above, in stable patients a preoperative MRI will also be performed which may provide additional relevant information for patient treatment.

Simultaneously, data from invasive multimodal neuromonitoring and laboratory values will be acquired and evaluated during the ICU stay after treatment.

All methods are validated by an international collaborative ring trial, as they are used in routine.

Finally, outcome scores like the mRS and the Glasgow Outcome Scale will be recorded.

INSTRUMENTS

➤ ***Multimodal Neuromonitoring***

- ICP-measurement, Raumedic, Münchberg, Germany
- Brain tissue oxygen and brain temperature, Licox, Integra, Plainsboro, New Jersey, USA
- Cerebral microdialysis, CMA, Stockholm, Sweden
- Alternatively tissue perfusion measurement, Hemedex, Cambridge, MA, USA

DISSEMINATION

A part of this study will most likely be assigned as a clinical Ph.D.-project for the residents at the Department of Neurosurgery.

STUDY POPULATION (SPECIMEN / TEST PERSON / PATIENTS)

IN- AND EXCLUSION CRITERIA

INCLUSION CRITERIA

- Posterior fossa lesions with anticipated prolonged neurointensive critical care
- Patients older than 18 years
- Informed consent if applicable (unconscious patients will be also enrolled)
- No existing exclusion criteria

EXCLUSION CRITERIA

- Coagulation disorders
- Age < 18 years
- Pregnancy

INFORMED CONSENT OF TEST PERSONS / PATIENTS

All patients harboring posterior fossa lesion who meet the inclusion criteria will be enrolled in the study.

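### Open infratentorial readings can prompt the search for the complications they are meant to detect, so the absolute detection rate is biased upward by an unknown amount

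*Combined protocol and SAP*

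**What the plan says.** **The claim.** The third item under HYPOTHESES reads: "The infratentorial multimodal monitoring immediately detects all relevant complications related to posterior fossa lesions including mass effect, local swelling, postoperative hematoma", followed by a list of ischemic and vascular events and ending "resulting in prompt therapeutic intervention if necessary". AIMS OF THE STUDY gives as a further aim the "immediate detection of any pertinent complications that are related to mass effect or swelling within the posterior fossa, leading to subsequent prompt intervention". QUESTIONS asks whether the monitoring can predict complications in time.

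**Who sees the readings.** INTERVENTION/EXAMINATION says that "data from invasive multimodal neuromonitoring and laboratory values will be acquired and evaluated during the ICU stay after treatment". The AIMS and HYPOTHESES sections also expect the infratentorial data to help steer ventilation, osmotherapy and positioning. The readings are thus open and in use.

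**How complications are looked for.** METHODS states that "all patients will undergo CT and/or MRI as standard of care within 72 hours after the intervention (the acute phase"), for the detection of procedure-related complications. After that, "an additional follow-up MRI will be performed if needed". For the MRI at different stages of treatment, INTERVENTION/EXAMINATION says "the indication for neuroimaging will be decided on a case-by-case basis". METHODS also requires all adverse effects to be noted, including those without clinical consequence.

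**What is recorded.** ANALYSIS (Data collection) classifies adverse events by mechanism and by outcome. The documents give no field for what prompted a diagnosis, no rule for dating onset, no definition of a probe signal, and no assessor unaware of the readings.

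**The concern.** A detection claim needs a reference for whether a complication occurred, and when, that does not depend on the test being judged. Here the test can influence the reference. A complication that the probe signals may be imaged and confirmed soon after the signal. One on which the probe stays silent may be looked for less, and if it is never found it is missing from the denominator. The recorded proportion detected then moves towards 100%. The recorded delay moves towards zero, because the missed and slowly recognised events are the ones lost.

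At stake is what can be concluded on the third hypothesis. The stated aims include making infratentorial monitoring standard of care, and a multicentre phase II is planned, so an inflated detection figure from the pilot would be carried forward. What prompted a diagnosis can be recorded reliably only at the time.

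**Working it through.** The plan states no sensitivity, lead time or complication rate, so there is no figure to reproduce. The calculations below are illustrations, and s, f and g are all assumptions.

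**Step 1: upward bias.** Let s be the true sensitivity and f the share of unsignalled complications found anyway, by the scan within 72 hours, clinical signs or another route. Take all signalled complications as confirmed. Then

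apparent sensitivity = s / (s + (1 − s)f).

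| f | s = 60% | s = 50% |
|---|---|---|
| 0.9 | 0.60/0.96 = 62.5% | 0.50/0.95 = 53% |
| 0.5 | 0.60/0.80 = 75% | 0.50/0.75 = 67% |
| 0.3 | 0.60/0.72 = 83% | 0.50/0.65 = 77% |
| 0.1 | 0.60/0.64 = 94% | 0.50/0.55 = 91% |

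The bias is absent only at f = 1. The scan in all patients and the rule to note all adverse effects push f up; discretionary later imaging pulls it down. The documents support no particular value.

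**Step 2: what the planned interval shows.** STATISTICAL ANALYSIS specifies Clopper-Pearson 95% intervals. If every recorded complication had been signalled, the lower limit would be 48% for 5 of 5 and 69% for 10 of 10. These limits carry sampling error only. With s = 60%, the chance that all of 5 recorded complications were signalled is 0.60⁵ = 0.08 at f = 1 and 0.75⁵ = 0.24 at f = 0.5, so a perfect score becomes three times as likely through ascertainment alone.

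**Step 3: why dropping probe-prompted complications is not a cure.** Let g be the share of signalled complications first established by a route other than the infratentorial reading. Restricting to complications not prompted by that reading gives

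sg / (sg + (1 − s)f).

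With s = 60% and f = 0.5:

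- g = 0.5: 0.30/0.50 = 60%
- g = 0.2: 0.12/0.32 = 37.5%
- g = 0.1: 0.06/0.26 = 23%

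This is unbiased only if g = f. If the team acts on early signals, g is likely to be small and the estimate too low. At f = 0.5 and g = 0.2 the two denominators give 75% and 37.5% around the assumed true 60%. They bracket the truth as long as g is below f.

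**Step 4: the comparison with the supratentorial probe.** Both probes run at the same time and both are open. If signals from either are followed up alike, the two apparent sensitivities share one denominator. Their ratio is then unbiased, although their absolute difference is inflated. Bias in the ratio needs unequal follow-up of the two probes, on which the documents say nothing.

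**The case against.** The strongest case against has four parts.

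- **Every patient is scanned within 72 hours, and all adverse effects are noted.** This stands as a limit on the bias: a silent complication can still be found, and because CT is allowed, the expected acute MRI drop-out need not lose the scan. But one scan at an unspecified time in the window cannot date onset or test immediacy, and vasospasm or delayed ischemia may come later. The rule on adverse effects governs reporting of what is found, not whether it is looked for.
- **No sensitivity or lead time is planned.** Correct: the outcome list in METHODS has neither. The hypothesis still cannot be addressed without them, which is a reason to define a signal, not to leave the matter open.
- **Who dates complications is not stated.** Also correct. That the team watching the probe does so is an inference from the single-centre setting, the open readings and the absence of a named assessor.
- **It is a small pilot.** METHODS gives 15 patients for phase I. That argues for a light remedy, and the one below is light.

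A reader might infer two stronger things: that the hypothesis is true by construction, and that the study favours the infratentorial over the supratentorial probe. The documents support neither. The scan in all patients can expose a miss, and Step 4 shows that the ratio can be unbiased. Treatment prompted by an early infratentorial signal could abort an event before the supratentorial probe shows it, but that is only a possibility.

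**Conclusion.** The concern holds for the absolute proportion detected and for the delay. Because the readings are open and intended to prompt action, and imaging beyond the one scheduled scan is discretionary, the first is biased upward and the second downward by an unknown amount. At an assumed true sensitivity of 60%, the apparent value runs from 62.5% (f = 0.9) to 94% (f = 0.1). This rests on signalled complications being confirmed more often than silent ones, which the plan permits but does not state. As written, the plan cannot separate true detection from complications found because the probe drew attention to them.

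**What to change.** 1. Add to the CRF, for each complication, what first prompted the diagnosis (scheduled scan, clinical sign, supratentorial reading or infratentorial reading) and the time.
2. For the third hypothesis, report detection and delay by trigger with two denominators: all complications, which tends to overstate sensitivity, and those not prompted by the infratentorial reading, which tends to understate it. Treat the pair as a rough bracket and do not use the second alone. Show separately the complications seen on the scheduled scan within 72 hours, whether or not the probe had signalled.
3. State in advance what counts as a probe signal. Fix the complication list and onset times before the traces are opened for analysis, and note that this blinds only partly, because the chart may reflect the readings.
4. Do not conclude that the probe detects all complications from those that it prompted.

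The cost is one CRF field, a signal definition, an analysis rule and an order-of-review rule. The price is small subgroups and wide intervals. Imaging and care do not change.

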Informed consent will be acquired from all patients for participation in the study during the study period.

All interventions and neuroimaging (e.g. MRI) will be performed as a part of routine clinical care and no modifications will be introduced in the treatment or the follow-up modalities currently used by the Department of Neurosurgery / Neuroradiology, except ^{31}P -MRS (see above).

CALCULATION OF THE NUMBER OF CASES

The study is designed as a prospective clinical trial (the sample of 30 patients was selected according to epidemiologic data and estimated annual incidence of posterior fossa lesions in Central Europe).

Regarding the complex patient cohort a high drop-out rate for MRI in the acute phase due to unstable patients with a consecutive infeasibility of MRI is to be expected.

ANALYSIS

Data collection

Clinical and procedural data will be collected prospectively. The adverse events are classified in three groups, according to their mechanism:

- * Lesion-related events
- * Intraoperative / intraprocedural (iatrogenic) events
- * Device-related problems

The outcome of adverse events is classified in four groups:

- * No clinical modification
- * Transient deficit(s)
- * Permanent deficit(s) (deficit(s) remaining at the 6-months follow-up)
- * Death

All-cause morbidity is defined as a modified Rankin score ≥ 3 . When the preoperative mRS was greater than 2, the all-cause morbidity is defined as any increase in the mRS value.

STATISTICAL ANALYSIS

The distribution of continuous variables will be described by using means and standard deviations, and discrete variables will be described as frequencies, percentages, and confidence intervals. The Clopper-Pearson exact method will be used to construct 95% confidence intervals (CIs).

The characteristics of both treatment groups will be compared by using Chi² test. All outcome results will be compared between the study groups by using a MannWhitneyU test, or Student t test where appropriate. P <0.05 is considered indicative of a statistically significant difference.

LITERATURE - REFERENCES

1. Mizunari T. [Clinical aspects and intracranial pressure monitoring in cases of traumatic posterior fossa hematoma]. *Nihon Ika Daigaku zasshi* 1990;57:334-343
2. Schroder R. [Expansive processes in the posterior cranial fossa and changes in intracranial pressure during the preoperative and postoperative period]. *Ceskoslovenska neurologie a neurochirurgie* 1982;45:306-314

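### The adverse-event classes do not separate the added infratentorial probe from the routine probe, so their counts alone may not describe the added-probe risk in the safety hypothesis

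*Combined protocol and SAP*

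**What the plan says.** All references are to the combined protocol and SAP.

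- **Hypotheses.** The first hypothesis is that posterior fossa monitoring is safe and feasible, "without any increased risk due to additional probes". The quantity of interest is harm from the added probe.
- **Study design, Methods.** Routine sensors usually lie in the right frontal lobe, at the lesion, or both. The study then adds more: "In case of posterior fossa surgery, additional probes (ICP / LICOX) will be placed into the surgical field". Aims of the study presents placement in the operative site as sparing the patient a second procedure.
- **Analysis, Data collection.** "The adverse events are classified in three groups, according to their mechanism". Besides lesion-related events, the groups are "Intraoperative / intraprocedural (iatrogenic) events" and "Device-related problems". A second scheme grades each event by its outcome, from no consequence to death. Neither scheme names a probe or a compartment.
- **Statistical analysis.** Frequencies get exact limits: "The Clopper-Pearson exact method will be used to construct 95% confidence intervals". The section also says that "The characteristics of both treatment groups will be compared", but the document defines no such groups and describes none without the added probe.
- **Sample size.** Methods gives 15 patients for phase I. Calculation of the number of cases gives 30.

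**The concern.** The safety hypothesis is about one device, and the classes sort events by mechanism. A patient with both probes can have an event from either, and both go into one undivided device-related class. Insertion harm from the added probe has two possible homes, because it arises in the operative field during the operation. The section has no rule for choosing between the intraoperative and the device-related class.

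The document shows the ambiguity itself. The same six harms (CSF leak, cranial nerve palsy, hematoma, infection, epilepsy, cerebral puncture) appear in the Present section as complications of pressure monitoring, and in Methods as procedure-related morbidity.

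At stake is the meaning of the reported proportion. Routine-probe events raise the device-related count, and insertion harm filed as intraoperative lowers it, so the net direction is unknown. Attribution that is not recorded when the event occurs may be hard to reconstruct, and a multicentre phase II is planned to follow.

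**Working it through.** The plan states no figure to reproduce here: no safety margin, reference rate or power calculation is tied to the classes, and the 30 patients are justified by incidence. The check therefore asks what a device-related count could mean.

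**Inputs from the document.** n = 15 (Methods) or 30 (Calculation of the number of cases); complication incidence of pressure monitoring, 1.1% to 7.7% (Present); Clopper-Pearson 95% limits (Statistical analysis).

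**Assumption, not in the document.** The 1.1% to 7.7% range applies per patient to the routine probe, independently between patients.

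**1. Can the routine probe alone produce a non-zero count?** P(at least one event) = 1 − (1 − p)^n.

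| p | n = 15 | n = 30 |
|---|---|---|
| 1.1% | 1 − 0.989^15 = 15% | 1 − 0.989^30 = 28% |
| 7.7% | 1 − 0.923^15 = 70% | 1 − 0.923^30 = 91% |

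The expected number of patients with a routine-probe event, n × p, is 0.17 to 1.16 at n = 15 and 0.33 to 2.31 at n = 30. A non-zero device-related count could thus arise with no contribution from the added probe, and the class would not show it.

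**2. What does a zero count mean?** For x = 0 the upper limit is 1 − 0.025^(1/n): 21.8% at n = 15 and 11.6% at n = 30. If every patient has the added probe, this bounds its device-classed harm. It does not bound insertion harm filed as intraoperative.

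**3. How far can filing move the proportion?** This illustration uses invented counts: 30 patients, all with the added probe, and two true added-probe events.

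| Situation | Device-related class | 95% limits |
|---|---|---|
| Both filed there | 2/30 = 6.7% | 0.8 to 22.1% |
| One filed as intraoperative | 1/30 = 3.3% | 0.1 to 17.2% |
| Both filed there, plus one routine-probe event | 3/30 = 10.0% | 2.1 to 26.5% |

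The intervals overlap widely. The issue is what the proportion describes, not its precision.

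**4. Denominator, only if some patients lack the probe.** Entry covers patients "in which any intracranial invasive intervention is indicated regardless of used technique or treatment modality", and Intervention/Examination allows treatment in the angiosuite, while Methods ties the added probes to posterior fossa surgery. If, purely as an assumption, one third lacked the probe, two events would be 2/20 = 10.0% (1.2 to 31.7%) instead of 2/30 = 6.7%. If every patient receives it, this step drops out.

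**The case against.** **The classes are one coding axis, not the whole record.** Methods requires every adverse effect to be noted, even without clinical consequence, and clinical and procedural data are collected prospectively. The document contains no case report form, so probe site might be recorded there. With 15 to 30 patients, each event could be reviewed individually. This stands, and it limits the point. A reader might infer that added-probe harm cannot be recovered at all; the document does not support that. Still, capturing an event is not attributing it, and nothing in the document requires attribution.

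**The lists of harms may already separate the sources.** The Methods list repeats the monitoring complications item for item, while Variables and parameters lists harms of lesion treatment such as iatrogenic rupture. The Present section also names CSF leak and cranial nerve dysfunction as specific worries with posterior fossa monitors. This narrows the gap, since event type hints at the source. It does not close it: Methods calls these events procedure-related, and the operation itself can cause them.

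**Exposure may be complete.** The Present section states the intention to monitor both compartments simultaneously. Intervention/Examination describes implantation whatever the treatment modality and refers to another study protocol for details. A reader might infer from the entry wording that some patients will lack the added probe; the document leaves that open. The denominator point is conditional.

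**Mechanism classes suit a pilot, and the missing comparator is the larger obstacle.** Both are fair. The remedy adds to the classes without replacing them, and it does not claim to supply a comparator.

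**Conclusion.** The concern holds in a limited form. Applied as written, the three classes give counts that may not describe the risk named in the first hypothesis. A non-zero device-related count could come from the routine probe only, and a zero count would leave insertion harm open. Case-by-case review may recover part of the information, but the plan does not require it.

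The size depends on assumptions. The 15% to 91% span in step 1 rests on applying the protocol's cited range to the routine probe; the shifts in steps 3 and 4 rest on invented counts and an invented exposure share. None of these is a document figure.

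A reader might also infer that coding events by probe would let the study confirm the hypothesis. It would not. No group without the added probe, reference rate or margin is defined, and even zero added-probe events leave a 95% upper limit of 21.8% (n = 15) or 11.6% (n = 30). The change should be made because it bears on a lead objective and is cheap; its absence does not invalidate the study.

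**What to change.** 1. In Data collection, for every adverse event in any of the three classes, record prospectively the probe location, whether that probe was routine or added for the study, and the attribution: added probe, routine probe, lesion or its treatment, or indeterminate. Location alone is not enough, because Methods also allows routine sensors at the lesion. State in advance that ambiguous surgical-field events (such as CSF leak, hematoma or cranial nerve palsy) will be reported both including and excluding them as added-probe events.
2. In Statistical analysis, report added-probe harms with the planned Clopper-Pearson interval among patients in whom the added probe was inserted or attempted. This equals all enrolled patients if every patient receives it.
3. State that the result estimates the added probe's complication rate and does not establish absence of increased risk, since the two treatment groups mentioned there are undefined and supply no reference.

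The cost is three items per event, one reporting rule and one denominator definition. The downsides are residual judgement when attributing events within a surgical field and possibly a smaller denominator with wider limits. Treatment and the interval method stay as planned.

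### The adverse-event groups have no class for events at the shared surgical and probe site whose cause cannot be separated, so probe harm can be filed as iatrogenic and missed

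*Combined protocol and SAP*

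**What the plan says.** Under ANALYSIS, Data collection, the rule is: "The adverse events are classified in three groups, according to their mechanism". The groups are "Lesion-related events", "Intraoperative / intraprocedural (iatrogenic) events" and "Device-related problems". None is defined further. There is no group for other or undetermined causes, and the plan does not say how, or by whom, the mechanism is assigned.

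Four other places bear on this:

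- STUDY DESIGN, METHODS puts the additional ICP and LICOX probes in the operative field. AIMS OF THE STUDY also describes the monitor as lying at the site of surgery.
- METHODS lists among the outcomes "peri- and postoperative morbidity and mortality, procedure-related morbidity including infection, hematomas, epilepsy, cerebral puncture, cranial nerve palsies, and CSF leaks". The risk paragraph under PRESENT names the same six complications, in the same order, as complications of ICP monitoring, and quotes an incidence of 1.1% to 7.7%.
- METHODS also states "All adverse effects will be noted and reported, even if no clinical consequence will ensue" and "Non-neurological complications such as cardiopulmonary complications will be documented separately".
- The first item under HYPOTHESES is that posterior fossa monitoring is safe and feasible and that the extra probes add no risk.

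**The concern.** The safety hypothesis is causal: it says that the probes add no risk. STATISTICAL ANALYSIS refers to comparing groups but does not describe them, and no probe-free comparison group appears anywhere in the protocol. The attribution of single events to the device therefore becomes a main source of evidence on probe risk.

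That attribution is hardest where it matters most. The probe is inserted during the operation, into the field of the operation. A hematoma, infection, cranial nerve palsy or CSF leak at that site may come from the surgery, from the probe or from both. Such an event meets the description of the iatrogenic group and also that of the device group. With no class for unresolved cause, the assessor has to choose. If the event goes under iatrogenic alone, it drops out of the device-related count and the probe looks safer than the data show. If it goes under device alone, a surgical complication may be charged to the probe.

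**Working it through.** The plan states no device-related rate, so there is no figure to reproduce. The check has two parts.

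**1. Do the groups separate the contested events?**

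| Event at the operative site | Listed as monitoring harm (PRESENT) | Listed as procedure-related (METHODS) | Groups that fit (Data collection) |
|---|---|---|---|
| Infection, hematoma, cranial nerve palsy, CSF leak | Yes | Yes | Iatrogenic and device-related |
| Epilepsy, cerebral puncture | Yes | Yes | Iatrogenic and device-related |

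All six items appear on both lists. The plan gives no rule that would place one of them in a single group.

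**2. How much does one event move the result?**

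Inputs: n = 15 (phase I, METHODS); n = 30 (CALCULATION OF THE NUMBER OF CASES); quoted incidence p = 1.1% to 7.7% (PRESENT); exact Clopper-Pearson 95% intervals (STATISTICAL ANALYSIS). Both sample sizes are carried because both stand in the document.

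Expected number of patients with a monitoring complication, n × p:

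- n = 15: 15 × 0.011 = 0.17 (0.165) to 15 × 0.077 = 1.16 (1.155)
- n = 30: 30 × 0.011 = 0.33 to 30 × 0.077 = 2.31

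Probability of at least one, 1 − (1 − p)^n:

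- n = 15: 15% to 70%
- n = 30: 28% to 91%

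Shift in the device-related rate when one event changes group, 1/n:

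- n = 15: 1/15 = 6.7 percentage points
- n = 30: 1/30 = 3.3 percentage points

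Device-related rate with its Clopper-Pearson 95% interval, for assumed counts:

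| Events counted as device-related | n = 15 | n = 30 |
|---|---|---|
| 0 | 0% (0 to 21.8) | 0% (0 to 11.6) |
| 1 | 6.7% (0.2 to 31.9) | 3.3% (0.1 to 17.2) |
| 2 | 13.3% (1.7 to 40.5) | 6.7% (0.8 to 22.1) |

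For zero events the upper limit is 1 − 0.025^(1/n), which gives 21.8% at n = 15 and 11.6% at n = 30.

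The quoted range is 7.7 − 1.1 = 6.6 points wide. At n = 15 a single reassigned event moves the estimate by about that whole width; at n = 30, by half of it.

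**The case against.** The strongest reply is that the grouping is by mechanism, not by time of onset, and that the second group is glossed as iatrogenic. A wound infection or leak caused by the craniotomy has an iatrogenic mechanism even if it appears days later. Much intensive-care morbidity is handled apart from the three groups, since METHODS says "Non-neurological complications such as cardiopulmonary complications will be documented separately". The six complications, and "peri- and postoperative morbidity and mortality", are also outcomes in their own right, so counts by type of event do not depend on the mechanism group.

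All of this stands, and it rules out a stronger reading. A reader might infer that postoperative complications of surgery or intensive care have no place in the scheme, that they are pushed into the device group, and that the device-related count is therefore meaningless. The documents do not support that. Nothing forces surgical events into the device group, and the iatrogenic group can take them, although its intraoperative/intraprocedural label leaves this unclear. An example in which several events known to come from the wound are all filed as device-related would only assume misfiling; the scheme does not cause it.

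It can also be said that the plan neither calls the groups mutually exclusive nor names the device-related rate as an endpoint. Both are true. But if double assignment is intended, the plan does not say how such events are counted. Counts by type show how many leaks or hematomas occurred, not how many the probe may have caused.

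The reply does not answer the overlap. Reading the second group broadly makes it more likely that an insertion hematoma is filed there and lost from the device count.

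**Conclusion.** The point holds in this form: the scheme has no class for events at the shared site whose cause cannot be separated, and the evidence that the probes add no risk depends on an undefined choice between two groups that both fit. One such choice is worth 6.7 percentage points at n = 15 or 3.3 at n = 30, where only about 0.17 to 1.16 or 0.33 to 2.31 monitoring complications are expected.

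This shows that the device-related rate is sensitive to attribution. It does not show that the rate is uninformative, or that events will in fact be misfiled.

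Assumptions: the quoted 1.1% to 7.7%, which is for ICP monitoring in general, is taken as an order of magnitude for the study probes; each affected patient is counted once; the event counts in the interval table are illustrative; and each event is put in one group, which the wording suggests but does not state.

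This is an inexpensive improvement that should be made, not a flaw that invalidates the study.

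**What to change.** In ANALYSIS, Data collection:

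1. Reword the second group so that it explicitly covers postoperative complications of the lesion's treatment as well as intraoperative and intraprocedural ones.
2. Add a group: surgery or probe, cause cannot be separated.

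In STATISTICAL ANALYSIS, report the device-related rate twice, each time with the Clopper-Pearson 95% interval already planned: device-related events only, and device-related plus inseparable events. Base the safety conclusion on both figures. For example, with no clear device event and one inseparable event in 15 patients, the report would give 0% (0 to 21.8) and 6.7% (0.2 to 31.9).

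The cost is one more category on the adverse-event form, one more table row, and an upper figure that will look less favorable. No treatment or follow-up changes. The groups should be settled before events are classified, because a cause recorded under the present three groups may be hard to revisit later.
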